**Figure 2.1: UX007G-CL301 Study Schematic**

**OBJECTIVES:**

The primary objective of the study is to:

- Evaluate the efficacy and safety of UX007 in the treatment of disabling paroxysmal movement disorders associated with Glut1 DS

**ENDPOINTS:**

Endpoints will be evaluated for UX007 and placebo treatment.

Primary Endpoint

The primary endpoint is the frequency of disabling paroxysmal movement disorders captured as movement disorder events observed during the Maintenance Period of treatment, as recorded by the subject/caregiver in an event-based daily Glut1 DS symptom diary.

### Secondary Endpoints

- Duration of disabling paroxysmal movement disorder events observed during the Maintenance Period of treatment, as recorded by the subject/caregiver in an event-based daily Glut1 DS symptom diary
- Walking capacity and endurance, as determined by the distance walked in 12 minutes during the 12 Minute Walk Test (12MWT)
- Patient/caregiver global impression of change in clinical status using the Clinical Global Impression – Improvement (CGI-I)
- Health-related quality of life assessing physical function, mobility, upper extremity function, fatigue, pain and social health using a PROMIS®-based questionnaire
- Cognitive function as measured by the Cambridge Neuropsychological Test Automated Battery (CANTAB) (assessed at select sites)

### Exploratory Endpoints

- Self-care, productivity, and leisure performance assessed by the Canadian Occupational Performance Measure (COPM)
- Physician global impression of change in clinical status using the Clinical Global Impression – Severity scale (CGI-S) and Clinical Global Impression – Improvement (CGI-I)
- Activity levels as measured by a wrist-worn actigraphy device at select study sites, where feasible. Endpoints include mean daytime activity, mean nighttime activity, and percent time in moderate or higher intensity activity
- Frequency and duration of disabling paroxysmal movement disorder events over time throughout the three-year open-label extension period
- PK data for UX007 metabolites

### Safety Endpoints

- Adverse events, including the subject incidence of adverse events (AEs), treatment related AEs, serious adverse events (SAEs), AEs leading to discontinuation and fatal AEs
- Clinically significant changes in vital signs, clinical laboratory test results, and electrocardiogram (ECG)
- Change in suicidal ideation & behavior assessment as measured by the Columbia Suicide Severity Rating Scale (C-SSRS)

**DIAGNOSIS AND CRITERIA FOR INCLUSION AND EXCLUSION:**

Individuals eligible to participate in this study must meet all of the following criteria:

- 1) Diagnosis of Glut1 DS confirmed by *SLC2A1* mutation
  - 2) Males and females, aged  $\geq 6$  years old at the time of informed consent
  - 3) At least 8 disabling paroxysmal movement disorder events in the 12 weeks prior to the Screening, by subject or caregiver report
- OR
- At least 6 disabling paroxysmal movement disorder events in any 6 consecutive week period, over the last 12 week period prior to the Screening, by subject or caregiver report
- 4) At least 4 disabling paroxysmal movement disorder events in the first 6 weeks of Run-in Period, reported in the daily electronic Glut1 DS symptom diary
  - 5)  $\geq 80\%$  compliance with daily electronic Glut1 DS symptom diary completion during the Run-in Period
  - 6) Not on KD, modified KD, or ketosis-inducing modified-fat diet for at least 3 months prior to Screening
  - 7) Plasma level of beta-hydroxybutyrate (BHB)  $\leq 1$  mmol/L (non-fasting) at Screening
  - 8) Provide written or verbal assent (if possible) and written informed consent by the patient (if an adult), or by a legally authorized representative after the nature of the study has been explained, and prior to any research-related procedures
  - 9) Must, in the opinion of the Investigator, be willing and able to complete key aspects of the study and be likely to complete the 22-week, placebo-controlled, treatment period
  - 10) Patient (or caregiver) must, in the opinion of the Investigator, be able to comply with accurate completion of the study daily Glut1 DS symptom diary
  - 11) Females of child-bearing potential must have a negative urine pregnancy test at Screening and Baseline and be willing to have additional pregnancy tests during the study. Females considered not to be of childbearing potential include those who have not experienced menarche, are post-menopausal (defined as having no menses for at least 12 months without an alternative medical cause) or are permanently sterile due to total hysterectomy, bilateral salpingectomy, or bilateral oophorectomy.
  - 12) Participants of child-bearing potential or fertile males with partners of child-bearing potential who are sexually active must consent to use a highly effective method of contraception as determined by the site Investigator from the period following the signing of the informed consent through 30 days after last dose of study drug

Individuals who meet any of the following exclusion criteria will not be eligible to participate in the study:

- 1) Any known hypersensitivity to triheptanoin or safflower oil that, in the judgment of the Investigator, places the subject at increased risk for adverse effects
- 2) Prior use of triheptanoin within 30 days prior to Screening

- 3) History of, or current suicidal ideation, behavior and/or attempts per C-SSRS at Screening or Baseline
- 4) Pregnant and/or breastfeeding an infant at Screening or Baseline
- 5) Participants unwilling or unable to discontinue use of a prohibited medication or other substance that may confound study objectives (Section 7.4.6.1 [MCT oil, barbiturates, pancreatic lipase inhibitors, KetoCal or other KD supplements, and/or KD])
- 6) Glut1 DS treatment regimen, including AEDs, should be stable for at least 30 days prior to Screening
- 7) Use of any investigational product (drug, medical food, or supplement, including medium chain triglyceride [MCT] oil, including coconut oil) within 30 days prior to Screening
- 8) Has a concurrent disease or condition, or laboratory abnormality that, in the view of the Investigator, places the subject at high risk of poor treatment compliance or of not completing the study, or would interfere with study participation or introduces additional safety concerns
- 9) Feeding or nutrition that, in the opinion of the dietitian, potentially affects consistent administration of study drug

**INVESTIGATIONAL PRODUCT, DOSE AND MODE OF ADMINISTRATION:**

UX007 (triheptanoin) is a liquid, intended for oral (PO) administration. UX007 is a colorless to yellow oil supplied in 1 L round, translucent high-density polyethylene (HDPE) or 1 L round amber colored glass bottles. Subjects will be dosed according to an age- and weight-based strategy (Table 2.1), up to a maximum daily administration of 130g. For subjects within 25% predicted BMI, actual body weight will be used to calculate the appropriate dose per the subject's age category. Adjusted body weight will be used for subjects with greater than 25% predicted BMI, to account for metabolic activity found in adipose tissue versus lean muscle. Adjusted body weight will be calculated in kilograms, using the following formula:

Formula 1# Adjusted Body Weight = Ideal Body Weight + [25% × (Actual Body Weight – Ideal Body Weight)]

UX007 dosing will be initiated using a 2-week titration schedule until the subject has reached his/her target total daily dose. If a subject has not reached the target total daily dose by the end of the 2-week titration period, dose titration should continue until the maximum tolerated dose is reached. For detailed information regarding dosing and titration, please refer to the Study Reference Manual.

**Table 2.1: Age-based UX007 Target Total Daily Dose**

Age Range	UX007 dose (g/kg/day) that is estimated equivalent to 30% total caloric intake
6 – 9 Years	2.5
10 – 14 Years	2
15 – 20 Years	1.5
21 and Over	1.2

The total daily dose will be divided into 4 equal doses mixed with food or drink (or formula, as appropriate), and administered PO or by gastronomy tube at breakfast, lunch, dinner, and before bed. The dose may be divided into smaller more frequent doses with food or drink as needed. The oil should not be taken without thoroughly mixing with food or drink. The dose should not be adjusted due to changes in age and/or weight during Periods 1 and 2.

**REFERENCE THERAPY, DOSE AND MODE OF ADMINISTRATION:**

Placebo will consist of safflower oil matching the attributes of UX007 oil. Dose level, titration, and mode of administration will be identical to that of UX007 during the double-blind Treatment Period.

#### **DURATION OF TREATMENT:**

The planned duration of treatment in this study is approximately 3.5 years, consisting of a 6-week Run- in Period, a 22-week placebo-controlled, crossover Treatment Period, followed by an optional, open-label Extension Period. All subjects who have completed the 22-week Treatment Period will be eligible for the Extension Period, during which all subjects will receive UX007; no placebo will be administered during the Extension Period. A Safety Follow-up Phone Call will be conducted 30-35 days after the last dose of UX007G-CL301 study drug. The last subject's Safety Follow-up Phone Call is the End-of-Study Time Point.

#### **CRITERIA FOR EVALUATION:**

##### **Primary and Secondary Efficacy Assessments:**

##### Disabling Paroxysmal Movement Disorders

- Subject Daily Glut1 DS symptom Diary: An event-based Glut1 DS symptom diary will allow the subject/caregiver to capture quantitative and qualitative aspects of disabling paroxysmal movement disorder events

##### Functional Outcome: Walking Capacity

- 12 Minute Walk Test (12MWT): The 12MWT is a variation of the 6MWT used to assess walking capacity and endurance as a functional outcome.

##### Health-related Quality of Life

- The Patient Reported Outcomes Measurement Information System (PROMIS®): A patient/proxy reported questionnaire selected from the PROMIS®-item bank to assess physical function, mobility, upper extremity function, fatigue, pain and social health.

##### Clinical Status: Patient Impression of Global Symptom and Disease Severity

- Patient impression of severity and change: The global impression of disease severity (using a 4-point Likert scale) at the start of the study and the degree of change in clinical status (CGI-I) as assessed by the patient/caregiver (7-point Likert scale) since the start of the study

##### Cognitive Function

- Cambridge Neuropsychological Test Automated Battery (CANTAB): Neuropsychological function measured using a standardized, computerized battery of tests designed to assess cognitive domains relevant to Glut1 DS subjects such as attention and memory tests. CANTAB will be performed at select study sites.

### **Exploratory Outcome Measures:**

Clinical Status: Physician Impression of Global Symptom and Disease Severity

- Physician impression of severity and change: Physicians will rate disease severity at Baseline (CGI-S) and continue to rate severity for the duration of the study using a 4-point Likert scale. Physicians will also record the degree of change in clinical status (CGI-I) using a 7-point Likert scale at post treatment visits.

Pharmacokinetic analysis of UX007 metabolites

- PK Analysis: a summary of PK analysis data and descriptive statistics will be completed

Activity Levels

- Actigraphy Device: A wrist-worn actigraphy device will assess the impact of Glut1 DS on activity levels during the last 10 days of the Run-In Period, the last 10 days of Treatment Period 1 and the last 10 days of Treatment Period 2. Endpoints include mean daytime activity, mean night time activity, and percent time in moderate or higher intensity activity. Actigraphy device will be used at select study sites, where feasible.

Qualitative Assessment

- Canadian Occupational Performance Measure: COPM will assess the impact of Glut1 DS on performance areas of self-care, productivity, and leisure.

### **Safety Assessments:**

- Incidence, frequency, severity, and relatedness of AEs and SAEs, including clinically significant changes from Baseline to scheduled time points in vital signs, clinical laboratory test results, and ECG
- Vital signs, weight, physical examination
- Pregnancy testing, suicidal ideation, via the Columbia Suicide Severity Rating Scale (C-SSRS)

### **STATISTICAL METHODS:**

A full description of the statistical evaluations will be provided in the Statistical Analysis Plan (SAP).

### **Sample Size:**

Based on the targeted patient population and eligibility criteria, it is estimated that the subjects receiving placebo will have a mean frequency of 8 disabling paroxysmal movement disorder events per 4 weeks, while subjects receiving UX007 will have a mean frequency of 4 disabling paroxysmal movement disorder events per 4 weeks, and a standard deviation of the difference of 7.4. A total sample size of 40 subjects (20 subjects in each treatment sequence) will have at least 85% power to detect such difference between UX007 and placebo groups. This sample size assumption incorporates a projected discontinuation rate of 15%.

**Analysis Populations:**

The efficacy analysis set will include all randomized subjects who received at least one dose of investigational product. Subjects will be analyzed as randomized.

The safety analysis set will include all subjects who receive at least one dose of investigational product, and subjects will be included in the treatment corresponding to the study treatment they actually received for the safety analysis.

**Efficacy Analysis:**

The primary analysis will compare the frequency of paroxysmal movement disorders captured as disabling movement disorder events (normalized to a 4 week rate) observed during the Maintenance Period of treatment with UX007 to the frequency of disabling movement disorders captured as movement disorder events (normalized to a 4 week rate) observed during the Maintenance Period of treatment with placebo, as recorded by the subject/caregiver in an event-based daily Glut1 DS symptom diary.

The primary endpoint will be analyzed based on the efficacy analysis set using a weighted ANCOVA model, with study baseline frequency of movement disorder as a covariate, treatment sequence, treatment group and period as fixed effects, and a random effect for subject within the sequence. When there is strong evidence suggesting that the normality assumption is not met, Wilcoxon rank-sum test will be considered as the primary analysis to assess the primary endpoint. The specific model will be defined in the SAP. The hypothesis that there is no difference in mean frequency of disabling paroxysmal movement disorder events per 4 weeks between treatment groups will be tested at the  $\alpha=0.05$  (2-sided) level.

For change-from-baseline efficacy endpoints, the baseline will be the last measurement taken prior to or on the first dose date of the first period for computation of the change from baseline value. The baseline measurement will be recorded before the dose is administered.

If the primary analysis for the primary efficacy endpoint is statistically significant, then a sequential testing strategy will be implemented for selected secondary efficacy endpoints in the following order:

- Duration of disabling paroxysmal movement disorder events
- Change from Baseline in 12MWT distance
- Patient/caregiver global impression of change in clinical status using the Clinical Global Impression – Improvement (CGI-I)

**Safety Analysis:**

All treatment emergent AEs (TEAEs) will be included in the analysis. Subject incidence of TEAE will be summarized by actual treatment received using the safety analysis set. Subject incidence of TEAE resulting in death, discontinuation and serious TEAE by actual treatment received will also be summarized. For C-SSRS, the percentage of subjects reporting any treatment emergent suicidal ideation and any treatment emergent suicidal behavior will be summarized descriptively by actual treatment received and visit week, respectively.

**Table 2.2: Schedule of Events (Screening; Run-in; Period 1; Washout; and Period 2)**

ASSESSMENT	Screening Visit Week -6	6-week Run-in Period	TREATMENT PERIOD 1			2-week Washout	TREATMENT PERIOD 2		
			Baseline 1	Phone Visits 1, 2, and 3	End of Treatment 1		Baseline 2 (End of Washout)	Phone Visits 4, 5, and 6	End of Treatment 2
			Week 0 (± 3 days)	Weeks 2, 4, and 6 (± 3 days)	Week 10 (± 3 days)		Week 12 ±3 days	Weeks 14, 16, and 18 (± 3 days)	Week 22 (± 3 days)
Informed Consent	X								
Inclusion/Exclusion Criteria	X		X						
Medical History	X								
SAFETY ASSESSMENTS									
Vital Signs	X		X		X		X		X
Physical Examination	X		X		X		X		X
Neurological Examination			X		X		X		X
Height	X		X		X		X		X
Weight	X		X		X		X		X
Columbia Suicide Severity Rating Scale (C-SSRS) 	X		X		X		X		X
Clinical Laboratory Tests 	X		X		X		X		X
Electrocardiogram (ECG)			X		X				X
Urine Pregnancy Test (If appropriate) 	X		X		X		X		X
Adverse Events 	X	X	X	X	X	X	X	X	X
Concomitant Medications	X	X	X	X	X	X	X	X	X

ASSESSMENT	Screening Visit Week -6	6-week Run-in Period	TREATMENT PERIOD 1			2-week Washout	TREATMENT PERIOD 2		
			Baseline 1	Phone Visits 1, 2, and 3	End of Treatment 1		Baseline 2 (End of Washout)	Phone Visits 4, 5, and 6	End of Treatment 2
			Week 0 (± 3 days)	Weeks 2, 4, and 6 (± 3 days)	Week 10 (± 3 days)		Week 12 ±3 days	Weeks 14, 16, and 18 (± 3 days)	Week 22 (± 3 days)
EFFICACY ASSESSMENTS									
Daily Glut1 DS Symptom Diary Training	X								
Daily Glut1 Symptom DS Diary Review			X	X	X		X	X	X
Daily Glut1 DS Symptom Diary Completion 		X	X	X	X	X	X	X	X
12MWT	X		X		X		X		X
CANTAB 	X		X		X		X		X
PROMIS ® Questionnaire			X		X		X		X
Patient: Clinical Global Impression of Severity			X						
Patient: Clinical Global Impression of Improvement					X		X		X
Physician: Clinical Global Impression of Severity			X		X		X		X
Physician: Clinical Global Impression of Improvement					X		X		X

ASSESSMENT	Screening Visit Week -6	6-week Run-in Period	TREATMENT PERIOD 1			2-week Washout	TREATMENT PERIOD 2		
			Baseline 1	Phone Visits 1, 2, and 3	End of Treatment 1		Baseline 2 (End of Washout)	Phone Visits 4, 5, and 6	End of Treatment 2
			Week 0 (± 3 days)	Weeks 2, 4, and 6 (± 3 days)	Week 10 (± 3 days)		Week 12 ±3 days	Weeks 14, 16, and 18 (± 3 days)	Week 22 (± 3 days)
Canadian Occupational Performance Measurement			X		X		X		X
Actigraphy Training 	X								
Actigraphy 		X			X				X
SPECIALTY LABORATORY ASSESSMENTS									
UX007 Metabolites 			X		X		X		X
BHB for ketosis detection	X		X		X		X		X
TREATMENT & DIETARY ASSESSMENTS									
Dietary Assessment and Consultation & Training on 3-day Diet Diary	X								
Dietary Assessment & Review of 3-day Diet Diary			X		X		X		X
Dietitian Consultation			X	X	X		X	X	X
Daily Study Medication Diary 			X	X	X		X	X	X
Review of Study Medication Diary			X	X	X		X	X	X
Daily Treatment with IP/Placebo			X	X	X		X	X	X

ASSESSMENT	Screening Visit Week -6	6-week Run-in Period	TREATMENT PERIOD 1			2-week Washout	TREATMENT PERIOD 2		
			Baseline 1	Phone Visits 1, 2, and 3	End of Treatment 1		Baseline 2 (End of Washout)	Phone Visits 4, 5, and 6	End of Treatment 2
			Week 0 (± 3 days)	Weeks 2, 4, and 6 (± 3 days)	Week 10 (± 3 days)		Week 12 ±3 days	Weeks 14, 16, and 18 (± 3 days)	Week 22 (± 3 days)
Dispense Study Drug			X				X		X 
Treatment Compliance & Accountability				X	X			X	X

1 Suicidal ideation and behavior will be assessed in subjects who are ≥ 10 years of age at each visit

2 For subjects ≥ 18 years old, lipid profile blood tests (LDL, HDL, total cholesterol, and triglycerides) will be assessed at Baseline 1 (Week 0), End of Treatment 1 (Week 10), and End of Treatment 2 (Week 22) after an overnight fast (8-12 hours).

3 For females of child-bearing potential

4 Plasma metabolite samples will be collected at time of SAE, if feasible

5 The definition of an AE also encompasses any increases in frequency or severity, or changes in type of Glut1 DS-associated symptoms, including but not limited to seizures, movement disorders, behavioral abnormalities, cognitive function, etc.

6 Glut1 DS symptom diary and study medication diary will be completed daily by the patient/caregiver. Review of the daily diaries will be performed at clinic or phone visits as indicated (or more frequently if needed)

7 CANTAB will be performed at select study sites

8 An actigraphy device will be worn on the last 10 days of the Run-in Period, the last 10 days of Treatment Period 1, and the last 10 days of Treatment Period 2 at select study sites, where feasible. Training for the actigraphy device will be provided at the Screening Visit.

9 Blood for plasma at Baseline Visits will be collected pre-dose. Blood for plasma at End of Treatment visits 1 and 2 will be collected approximately 90 minutes post dose.

10 Beginning at Week 22, all subjects will be dispensed UX007 for the open-label Extension Period

**Table 2.3: Schedule of Events (Extension and Safety Follow-up)**

ASSESSMENT	EXTENSION		END OF TREATMENT VISIT	EARLY TERMINATION VISIT	SAFETY FOLLOW-UP
	Extension Visits	Extension Phone Visits	End of Treatment Visit	Early Termination Visit	Follow-up Phone Call 
	Weeks 34, 58, 82, 106, 130, 154 (± 2 weeks)	Weeks 26, 30, 46, 70, 94, 118, 142 (± 2 weeks)	Week 178 (±2 weeks)	Final Dose (+4 weeks)	30-35 Days after Final Dose
SAFETY ASSESSMENTS					
Vital Signs	X		X	X	
Physical Examination	X		X	X	
Neurological Examination	X		X	X	
Height 	X		X	X	
Weight	X		X	X	
Columbia Suicide Severity Rating Scale (C-SSRS) 	X		X	X	
Clinical Laboratory Tests 	X		X	X	
Electrocardiogram (ECG) 	Weeks 58, 106, and 154 Only			X 	
Urine Pregnancy Test (If appropriate) 	X		X	X	
Adverse Events 	X	X	X	X	X
Concomitant Medications	X	X	X	X	X
EFFICACY ASSESSMENTS					
Daily Glut1 DS Symptom Diary review	X	X	X	X	
Daily Glut1 DS Symptom Diary completion 	X	X	X	X	
12MWT	X		X	X	
CANTAB 	X		X	X	

ASSESSMENT	EXTENSION		END OF TREATMENT VISIT	EARLY TERMINATION VISIT	SAFETY FOLLOW-UP
	Extension Visits	Extension Phone Visits	End of Treatment Visit	Early Termination Visit	Follow-up Phone Call 
	Weeks 34, 58, 82, 106, 130, 154 (± 2 weeks)	Weeks 26, 30, 46, 70, 94, 118, 142 (± 2 weeks)	Week 178 (±2 weeks)	Final Dose (+4 weeks)	30-35 Days after Final Dose
Patient: Clinical Global Impression of Improvement	X		X	X	
PROMIS ® Questionnaire	X		X	X	
Physician: Clinical Global Impression of Severity	X		X	X	
Physician: Clinical Global Impression of Improvement	X		X	X	
Canadian Occupational Performance Measure	X		X	X	
SPECIALTY LABORATORY ASSESSMENTS					
UX007 Metabolites 	Week 34 Only 				
BHB for ketosis detection	X		X	X	
In-clinic dose	Week 34 Only 				
TREATMENT & DIETARY ASSESSMENTS					
Dietary Assessment/ Consultation & Review of 3-day Diet Diary	X		X	X	
Daily Study Medication Diary 	X	X			
Review of Study Medication Diary	X		X	X	
Daily Treatment with IP	X	X			
Dispense Study Drug	X				

ASSESSMENT	EXTENSION		END OF TREATMENT VISIT	EARLY TERMINATION VISIT	SAFETY FOLLOW-UP
	Extension Visits	Extension Phone Visits	End of Treatment Visit	Early Termination Visit	Follow-up Phone Call 
	Weeks 34, 58, 82, 106, 130, 154 (± 2 weeks)	Weeks 26, 30, 46, 70, 94, 118, 142 (± 2 weeks)	Week 178 (±2 weeks)	Final Dose (+4 weeks)	30-35 Days after Final Dose
Treatment Compliance & Accountability	X	X	X	X	

- 1 Height only to be collected in the extension period for subjects under the age of 20
- 2 Suicidal ideation and behavior will be assessed in subjects who are ≥ 10 years of age at each visit
- 3 For subjects ≥ 18 years old, lipid profile blood tests (LDL, HDL, total cholesterol, and triglycerides) will be at clinic extension visits after an overnight fast (8-12 hours).
- 4 ECG will be performed at Weeks 58, 106, 154 during the Extension Period (or Early Termination, if applicable). ECG will not be performed at Early Termination visit if the assessment was conducted within 3 months of termination.
- 5 For females of child-bearing potential
- 6 The definition of an AE also encompasses any increases in frequency or severity, or changes in type of Glut1 DS-associated symptoms, including but not limited to seizures, movement disorders, behavioral abnormalities, cognitive function, etc.
- 7 Glut1 DS symptom diary and study medication diary will be completed by the patient/caregiver. Review of the daily diaries will be performed at clinic or phone visits as indicated.
- 8 CANTAB will performed at select study sites.
- 9 Blood for plasma metabolites will be collected at the Week 34 visit only (pre-dose (within 15 minutes) and at [± 5 minutes] 30, 90, and 120 minutes post dose).
- 10 Safety-Follow-up Phone Call to be conducted 30-35 days after last dose of UX007G-CL301 study drug, even in cases of Early Termination. The site personnel will initiate this safety follow-up telephone call to collect information on any ongoing or new AEs, serious adverse events (SAEs), and concomitant medications. Appropriate follow-up should continue until all safety concerns, in the Investigator's opinion, are resolved.

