At the end of the Run-in Period, eligible subjects will be randomized (1:1 ratio) to one of two treatment sequences (UX007/placebo or placebo/UX007). At Randomization, subjects will begin a 10-week double-blind Treatment Period 1. Treatment Period 1 will consist of a 2-week titration period and an 8-week Maintenance Period. At the end of Treatment Period 1, subjects will discontinue treatment and begin a 2-week washout period to minimize any potential carryover effect. Subjects will crossover to the second randomized, double-blind treatment assignment (placebo to UX007, UX007 to placebo) for an additional 10 weeks during Treatment Period 2. Treatment Period 2 will consist of a 2-week titration period and an 8-week Maintenance Period. At the end of the blinded crossover period (Week 22), all active subjects will have the option of rolling into the open-label Extension Period, to continue UX007 treatment for up to 3 years or until one of the following occurs: the subject withdraws consent, the subject is discontinued from the study at the discretion of the Investigator, the study is terminated, or until commercial availability of the study drug in a subject's region, whichever occurs first. Long-term safety and maintenance of effect of UX007 will be assessed during the open-label Extension Period. A study schematic is provided in Figure 2.1. A Safety Follow-up Phone Call will be conducted 30-35 days after the last dose of UX007G-CL301 study drug.

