### 7.3.3 Removal of Subjects from Therapy or Assessment

In accordance with the Declaration of Helsinki, subjects have the right to withdraw from the study at any time for any reason. The Investigator and Ultragenyx also have the right to remove subjects from the study. Ultragenyx must be notified of all subject withdrawals as soon as possible. Ultragenyx also reserves the right to discontinue the study at any time for either clinical or administrative reasons and to discontinue participation of an individual subject or Investigator due to poor enrollment or noncompliance, as applicable.

Subjects will be removed from the study for the following reasons:

- An illness or AE that, in the judgment of the Investigator or Ultragenyx, might place the subject at risk or affect study conduct (Section 8.5.4)
- Pregnancy of the subject or partner of a subject

Subjects may be removed from the study for the following reasons:

- Initiation of KD or similar diet resulting in a BHB > 1 mmol/L
- Use of prohibited medications
- At the request of the subject (withdraws consent), Investigator, or Ultragenyx, for administrative or other reasons
- Protocol deviation or noncompliance

If a subject discontinues from the study prior to End of Treatment 2, every reasonable effort should be made to perform the Early Termination Visit procedures as soon as possible after the last dose of investigational product, and at most, within four weeks of discontinuation. Subjects who withdraw or are removed from the study after receiving study drug may be replaced on a case-by-case basis, at the discretion of Ultragenyx.

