#### **7.5.4.6 Electrocardiogram**

A standard 12-lead ECG will be performed at a resting heart rate during the Baseline 1 visit (Week 0), End of Treatment 1 (Week 10), and End of Treatment 2 (Week 22), and every 48 weeks throughout the Extension Period (Weeks 58, 106, and 154 or Early Termination visit, if applicable). ECG will not be performed at the Early Termination visit if the assessment has been performed within 3 months of termination. ECG results will be read locally by qualified personnel. Abnormal findings and clinically significant changes from baseline will be recorded as AEs.

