8.9.4 Electrocardiogram

The results from ECG (normal and abnormal) will be summarized.

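### The three-month waiver of the Early Termination ECG lets a baseline or other-treatment ECG stand in for subjects who stop during double-blind dosing

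*Protocol*

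**What the plan says.** Protocol Table 2.2 and Section 7.5.4.6 plan ECGs in the double-blind phase at Baseline 1 (Week 0), End of Treatment 1 (Week 10) and End of Treatment 2 (Week 22). There is none at Screening or at Baseline 2 (Week 12). Extension ECGs follow at Weeks 58, 106 and 154.

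Section 7.3.3 covers early leavers: "If a subject discontinues from the study prior to End of Treatment 2, every reasonable effort should be made to perform" the Early Termination procedures as soon as possible after the last dose, and "at most, within four weeks of discontinuation". Table 2.2 has no Early Termination column. The only one is in Table 2.3, where the ECG is listed subject to footnote 4: "ECG will not be performed at Early Termination visit if the assessment was conducted within 3 months of termination". Section 7.5.4.6 says the same: "ECG will not be performed at the Early Termination visit if the assessment has been performed within 3 months of termination". SAP Appendix C, footnote 4, repeats it. None of the three places requires the earlier ECG to have been recorded on the treatment being stopped, and none limits the waiver to the extension.

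Clinically significant ECG change is a safety endpoint (Protocol Section 6.1.4; the SAP lists ECG in Section 4.4). The whole planned analysis is in SAP Section 8.9.4: "The results from ECG (normal and abnormal) will be summarized".

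**The concern.** A recency waiver is reasonable when the recent ECG tells the same story as the one it replaces. In a crossover with 10-week periods and one ECG at the end of each, it often does not. The last planned ECG before a mid-period stop is either the study baseline or a recording at the end of the other treatment, and both are recent enough to trigger the waiver.

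The waiver then removes the only planned ECG that could follow dosing with the treatment being stopped. A Period 1 dropout has no planned post-dose ECG at all. A placebo/UX007 subject who stops in Period 2 has none after UX007. These subjects stop early, possibly for an adverse event, so this is where a missing safety reading is least welcome. Vital signs, physical and neurological examinations and laboratory tests in the same Early Termination column carry no waiver of this kind.

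**Working it through.** The documents give no figure of their own to reproduce here; the check is on the visit schedule.

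**Inputs.** Planned ECG days: 0, 70 and 154 (Weeks 0, 10 and 22). Period 1 dosing before the Week 10 visit: stop days 1–69. Washout: days 70–83. Period 2 dosing before the Week 22 visit: stop days 84–153. Three months: 365.25 / 4 = 91.3 days. Early Termination visit: up to 28 days after discontinuation (Section 7.3.3).

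**Pre-dose status of Week 0.** The documents do not say in words that this ECG precedes the first dose. I infer it: the visit is Baseline 1, study drug is first dispensed there, and Section 7.5.4.6 judges later ECGs against baseline.

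**Counted to discontinuation on day d.**
- Period 1: gap = d − 0, at most 69 days. Waived on 69 of 69 days, on the baseline ECG.
- Period 2: gap = d − 70, from 14 to 83 days. Waived on 70 of 70 days, on the ECG from the other treatment.
- Washout: gap = d − 70, from 0 to 13 days. Waived on 14 of 14 days, but here the Week 10 ECG does reflect the treatment just stopped.

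With both ±3-day visit windows at their extremes, the largest gaps are 70 + 6 = 76 days and 84 + 6 = 90 days, still under 91.3. Three calendar months can be as short as 89 days, so the 90-day extreme could just escape on that count; the nominal maximum of 83 could not.

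**Counted to an Early Termination visit w days after discontinuation.** The ECG is waived if d + w ≤ 91.3 (Period 1) or d + w − 70 ≤ 91.3 (Period 2).

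| Visit delay w | Period 1 stop days waived | Period 2 stop days waived |
|---|---|---|
| 0 or 7 days | 69/69 | 70/70 |
| 14 days | 69/69 | 64/70 |
| 21 days | 69/69 | 57/70 |
| 28 days | 63/69 | 50/70 |

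For w = 28: d ≤ 63.3 gives days 1–63, and d ≤ 133.3 gives days 84–133.

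**Reach.** Projected discontinuations: 0.15 × 40 = 6, an upper figure because some may leave during washout. For subjects who stop during dosing:

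| Sequence | Stops in Period 1 | Stops in Period 2 |
|---|---|---|
| UX007/placebo | no UX007 ECG | has a UX007 ECG (Week 10) |
| placebo/UX007 | never took UX007 | no UX007 ECG |

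Two of the four cells lose a UX007 ECG. If all 6 stopped during dosing and were spread evenly over the cells (an assumption; the documents do not say when subjects leave), that is 6 × 2/4 = 3 subjects.

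**The case against.** The three passages agree with one another, so this is a repeated and apparently deliberate choice, not a contradiction. Little analysis depends on it: SAP Section 8.9 plans no statistical comparisons for safety data, and the ECG summary is only normal against abnormal. Early leavers still have vital signs, examinations, laboratory tests and adverse event collection at Early Termination, then the safety call at 30–35 days, and the data monitoring committee reviews safety. An Early Termination ECG may also be taken up to 4 weeks after the last dose. The design relies on a 2-week washout to minimise carryover, so a late ECG may describe an off-drug state.

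All of this stands, and it makes the point minor. It does not remove it: none of the other assessments is an ECG, the protocol asks for the visit as soon as possible, and SAP Section 7.4 already has a rule for mapping Early Termination results to scheduled visits.

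A reader might infer more than the documents support:
- *That every double-blind dropout lacks an ECG on the treatment stopped.* Washout leavers have the Week 10 ECG, and SAP Section 8.9.1 assigns washout adverse events to the Period 1 treatment.
- *That the ECG summary covers only subjects who stayed on treatment.* Period 2 and washout dropouts still contribute a Week 10 ECG.
- *That all six projected dropouts are affected.* That needs every one to stop during dosing. It also needs discontinuation to be the reference date, or a prompt visit. *Termination* is not defined.
- *That the rule was written with the 48-week extension spacing in mind.* Neither document says so.

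**Conclusion.** The point holds for subjects who stop during dosing in the double-blind phase. Followed exactly, with a prompt visit, the waiver applies to every such subject on an ECG that does not reflect the treatment being stopped. If *termination* means the visit date, visits delayed by 14 days or more let some late-period dropouts through, but most stop days remain covered even at the 28-day limit.

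The size is small: at most about 6 of 40 subjects without an ECG after the treatment they stopped, and fewer without one after UX007. No efficacy result or test is touched. The conclusion rests on the projected 15% discontinuation, on the Week 0 ECG being pre-dose, and on no unscheduled ECG being taken. I rate it minor, but worth correcting because it concerns a listed safety endpoint.

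**What to change.** Reconcile the waiver in Protocol Table 2.3 (footnote 4), Protocol Section 7.5.4.6 and SAP Appendix C (footnote 4) with the double-blind ECG schedule and the ECG safety endpoint, so that a baseline ECG, or one from the other treatment period, does not count towards the three months. In the same places, state whether *termination* is the last dose or the visit date.

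In SAP Section 8.9.4, report Early Termination ECGs with the time since last dose, because some may be recorded up to 4 weeks off drug and should not be read as on-treatment values.

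The cost is a short wording change in each place and up to about six standard ECGs, at a visit that already lists the ECG.
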